#### Compliance (%) during the double blind period

The overall compliance will be computed:

- COMP = CD/CT
  - CD : Number of tablets Dispensed Unused Tablet number returned, at the end of the double blind period

With Number of tablets dispensed at each visit according to the dose:

 CT : Number of Treatment Exposure Day\* Theoric Number of tablets per day, at the end of the double blind period

Amount predicted according the daily dose:

- 5 mg: 1 tablet of 5 mg \* treatment duration in days at this dose
- 10 mg: 2 tablets of 5 mg \* treatment duration in days at this dose
- 20 mg: 1 tablet of 20 mg \* treatment duration in days at this dose
- 40 mg: 2 tablets of 20 mg \* treatment duration in days at this dose

Between the V2 and V3 visits there is a dose increase (5 => 10 mg). According to the collected data it's impossible to know when the patient took 1 tablet more. So for the compliance, for the CT computation, the assumption that 1 tablet is taken during the first seven days and 2 after will be done between V2 and V3.

Compliance will be considered as missing for patients with premature withdrawal during the double blind period without information about the number of tablets returned at the premature withdrawal visit.

Age (in classes)
 Two ago classos will I

Two age classes will be computed:

- [6-11] years,
- o [12-18[ years,
- BMI

For weight, only one decimal should be kept for the analysed values.

The Body Mass Index is calculated at a visit in the database:

BMI  $(kg/m^2) = Weight (kg) / (Height (cm) x 0.01)^2$ ,

using the height and the weight recorded at the corresponding visit.

The result is rounded to one decimal place.

The BMI Classes refer to the statistical methodology used by the WHO standards.

This methodology is computed according to the sex and the age in months.

For each visit, the calculated age at the concerned visit is taken into account.

- If it's a boy, the reference table is the table « BMI-for-age\_WHO.xls» sheet « Boys »
- If it's a girl, the reference table is the table « BMI-for-age\_WHO.xls» sheet « Girls » According to these tables:
- If the BMI < -2SD then BMI class= « underweight »
- If the -2SD ≤ BMI ≤ +1 SD then BMI class= « normal range »
- If the +1SD < BMI ≤ +2 SD then BMI class= « overweight »
- If the BMI > +2 SD then BMI class= « obese »

# 4.1.5.5 Efficacy data

## Ullanlinna Narcolepsy Scale (UNS)

For the subscores recalculation the correspondence between the character and numerical modalities:

For questions about « Knees unlocking symptoms » (UNS01), « Mouth opening symptoms » (UNS02), « Head nodding symptoms » (UNS03) and « Falling down symptoms » (UNS04) :

Character	Numeric
NEVER	0
1-5 TIMES DURING LIFETIME	1
MONTHLY	2
WEEKLY	3
DAILY OR ALMOST DAILY	4

For questions about « Fall asleep during reading » (UNS07), « Fall asleep during travelling » (UNS08), « Fall asleep during standing » (UNS09), « Fall asleep during eating » (UNS10) and « Fall asleep during other unusual » (UNS11) :

Character	Numeric
NEVER	0
1-5 TIMES DURING LIFETIMES	1
MONTHLY	2

_ `		(	
	DAILY OR ALMOST DAILY		4
	WEEKLY		3

For the question « Fast to feel asleep the evening » (UNS05):

Character	Numeric
>40 MIN.	0
31-40 MIN.	1
21-30 MIN.	2
10-20 MIN.	3
<10 MIN.	4

For the question « Sleep during the day» (UNS06):

Character	Numeric
NO NEED	0
I WANTED BUT CANNOT SLEEP	1
2 DAYS OR LESS EACH WEEK	2
3-5 DAYS EACH WEEK	3
6-7 DAYS EACH WEEK	4

Two sub-scores are derived:

- ✓ The cataplexy score:
  - Sum of the first four items (UNS01 + UNS02 + UNS03 + UNS04)
- ✓ The EDS score:

Sum of the seven other items (UNS05 + UNS06 + UNS07 + UNS08 + UNS09 + UNS10 + UNS11)

CGI

Two scores are computed within the ranges of 0 -7 (0 = Not assessed):

- o Global Improvement (CGI-I) score
- o Severity (CGI-S) score

# The response to treatment according to CGI-I is derived at a visit as:

- If CGI-I score = 1 (very much improved) or 2 (much improved) or 3 (minimally improved) then response to treatment at the visit = Yes.
- If CGI-I score > 3 then response to treatment at the visit = No.
- Otherwise, response to treatment at the current visit is not calculated.

# Pediatric Daytime Sleepiness Scale scores (PDSS)

The response to treatment according to PDSS is derived at a visit as a score reduction of 3 Between the baseline and the final value:

- If  $PDSS_B-PDSS_F \ge 3$  then response to treatment at the visit = Yes.
- If PDSSB-PDSSF < 3 then response to treatment at the visit = No.
- Otherwise, response to treatment at the current visit is not calculated.

## Maintenance of Wakefulness Test 30-minute version

For this assessment the four test have been considered. Therefore, arithmetic means and sum on these 4 tests are computed.

**Mean value for each latency parameter**, in minutes, for a visit, will be estimated as the arithmetic mean of the 4 tests.

**Before this mean computation each latency parameter** (sleep onset, Stade I, Stade II, stade III and SP) must be recalculed to take into account the "Awake" status and the test duration:

- For a test, if "Awake"= "yes" then the sleep onset latency has to be considered at 30min (even if another value is entered).

- If a reported value is greater than 30min this value will be censured at 30min.

Number of Sleep onset in SP for a visit, will be computed as the sum of Yes (=1) of the 4 tests.

A survival response will be computed according to the "sleep onset latency" recalculed:

- Non-response (0=patient remained awake until 30 minutes) = Mean sleep onset latency ≥ 30min.
- Response (1=patient falling asleep before 30 minutes) = Mean sleep onset latency < 30min.

- Patient sleep diary
- Rate of cataplexy (WRC), Number of diurnal involuntary sleep attacks and episodes of severe daytime sleepiness (NSAE) and Number of hallucinations and sleep paralysis episodes (NHS) are weekly ratio computed as :

[Number of episodes of the concerned parameter in the period / Number of days in the period] \* 7

Whith Number of days in the period= Date of the last visit of the period - Date of the first visit of the period + 1

Results are rounded to to the nearest integer number.

- Night duration (NightD), in hours, is calculated as:

Wake-time (morning) - Hour of bedtime (evening)

The mean of night duration per day during the studied period is computed as:

Sum of night duration in the period / Number of days in the period

Whith Number of days in the period= Date of the last visit of the period - Date of the first visit of the period + 1

The result is rounded to one decimal place.

In case of several hours at the same date the following rule will be applied:

- For wake-time the last hour will be kept
- For bedtime the first hour will be kept

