## 4.1.3 IMP groups comparison

# 4.1.3.1 Main Inferential model

Unless otherwise specified, all the endpoints referred in detail in the following section will be analyzed according the same statistical model allowing a comparison of results between the studied endpoints. The significance of the difference between the IMP compared with placebo will be assessed through a general model of analysis of Covariance (ANCOVA) in which the studied endpoint at final time (noted Yf) constitutes the dependent variable of the model. Independent variables are (1) the baseline value of the studied endpoint (noted Yb) analyzed as a fixed covariate, (2) the treatment effect (Noted Trt) coded 0 (placebo) or 1 (IMP) (cell mean contrast formulation), and (3) the center considered as a random factor of the intercept constituted by a fixed part  $k_0$  and a random component N(0, $\sigma_c$ ). This model is summarized by the following expression:

 $Y_{if} = (k_0 + \zeta) + k_b Y_b + k_t Trt + \epsilon_i \quad \epsilon_i = N(0, \sigma) \text{ and } \zeta = N(0, \sigma_c) \text{ [general Model -1]}$ 

Note 1-This model does not assume a treatment-baseline interaction term (as required in CPMP, 2003). Our decision of using center as a random factor is justified by the useless estimate of each center, in focusing on the measurement of the standard deviation of the intercept. The treatment will be considered as fixed factor without center random component.

Note 2- This model is a Linear Mixed Model (LMM) as it combines random and fixed factors, assumes linearity of baseline and hypothesizes the studied endpoint distributed according to a normal (Gaussian) distribution. This model constitutes the main model used in this trial for all the studied endpoints unless otherwise specified.

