# 4.1.3.2 Multiple Testing

# (ICH E3; 9.7.1, 11.4.2.5. ICH E9; 2.2.5, FDA-2017)

The main analysis is defined as the analysis of covariance following general Model 1 [section 4.1.3.1] conducted on the main selection (FAS), on the primary endpoint (UNS) considered as a global endpoint aggregating both EDS and cataplexy symptoms. Secondary endpoints will be PDSS and the UNS-CTP subscale measuring the IMP effect on EDS and cataplexy, respectively. Two other secondary endpoints will be the weekly rate of cataplexy measured by the patient diary (WRC) and the MWT. All the other endpoints will be considered as exploratory and supportive.

The main endpoint (UNS) and the four secondary endpoints necessitate 5 tests. We will use the fixedsequence strategy testing the endpoints in the pre-defined order UNS, PDSS, UNS-CTP, WRC and MWT, each one tested at two-sided  $\alpha$ =.05 significance, moving to the following endpoint conditionally to a significant difference reached on the previous endpoints (FDA, section C.5). This strategy protects the results with type 1 risk bounded by P=.05.

Our choice is justified as follows: UNS constitutes a global appraisal of both EDS and cataplexy in pediatric narcolepsy and must regarded as a relevant general first endpoint. PDSS and UNS-CTP are validated scales to measure EDS alone and cataplexy alone, respectively. Conditionally to a significant effect on the main UNS endpoints, the effect of the IMP will be assessed on the two symptoms, separately. Finally MWT and WRC are alternative endpoints to measure EDS and cataplexy, respectively, and will be assessed conditionally to the significance obtained on UNS, PDSS and UNS-

CTP. Besides, EDS is a more frequent symptom, thus it was tested before cataplexy, and PDSS and UNS-CTP were shown with a higher power than MWT and WRC, respectively [ref-validation]

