#### 4.1.4 Missing data

#### 4.1.4.1 General considerations

(ICH E3; 9.7.1, 11.4.2.2. ICH E9; 5.3. EMA Guideline on Missing Data in Confirmatory Clinical Trials) Missing data will be imputed for five main endpoints of this study (UNS, PDSS, UNS-CTP, WRC and MWT). For the other endpoints no missing value will be imputed.

A Multiple Imputation (MI) procedure will be used to impute the missing evaluations, as a prior step, assuming that those patients would be in their randomized arm. The partially complete datasets will be generated with a model including the following covariates age, gender and the main model components (section 2.2).

A total of 100 imputed partially complete datasets will be generated.

MI inference involves 3 consecutives phases:

- 1/ Imputation step:

The missing pattern is supposed to be monotone, so the regression method will be used to impute missing data.

The partially complete datasets will be generated with a model including age, gender factors and taking into account the baseline score of the primary endpoint, based on patient which every postbaseline measurement available. It is of note that this imputation step might be preceded by one MI approach based on MCMC method, in case of arbitrary missing pattern. A total of 100 imputed partially-complete datasets will be generated.

The mean MD imputation will based on Missing at Random (MAR) corresponding to the hypothesis that missingness is assumed independent of the outcome, or to estimate a "de jure" (per protocol) estimand, censoring after any protocol deviation. This hypothesis was considered as the most likely in this particular context.

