Despite the likelihood of this option, a secondary MD imputation will be conducted according to the Missing at Random hypothesis (MNAR), for which several options to construct the joint distribution of the observed and unobserved data have been proposed, each reflecting a different MNAR mechanism (Carpenter et al., 2013). This appropriate choice was discussed in the general context of narcolepsy. We assumed that after dropping out, participants from the active arm have the same outcomes as the reference group individuals, hypothesizing that the treatment effect is lost after the individual leaves the study. This option is called Jump to reference (J2R), after dropout, the participant's conditional outcomes are associated to those of the control arm. The joint distribution is a Multivariate Normal model with mean parameters from the randomised arm until date of interruption (Di) and from the reference group afterward. The covariance matrix corresponds to the parameters from the randomised arm until Di and to the reference group for the conditional components of the post-dropout variables, given the pre-dropout measurements.

Concerning the J2R, the jump-to-placebo approach will be set up for these patients' imputations, by using the %mistep macro from James Roger (https://www.lshtm.ac.uk/research/centres-projects-groups/missing-data#dia-missing-data, zip file MISTEP20180327).

Usualy, a sequence of %mistep is run, the subsequent models include the residuals of the previous model. In this study only one model will be used (for the endpoint value imputation).

In case of imputed data outside the range, the minimun or the maximun bound will be used.

This macro will be used because no SAS procedure are currently available to perform the jump to reference approach.

- 2/ Analysis step:

The same analysis as described above will be applied to each of the 100 imputed datasets.

- 3/Combination step:

Statistical inferences will be generated by combining results from 100 analyses using Rubin's formulae (Rubin, 1987).

The multiple imputation estimator of the difference between active treatment and placebo is the average of the individual 100 estimators. The variance of the estimator is the combination of the between and within-imputation variability (Kenward & Carpenter, 2007).

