# 4.1.5 Derived variables

## 4.1.5.1 General definitions

The following definitions will be considered:

- Analysable value will be defined as any non-missing value.
- Baseline value will be defined as :
  - For UNS, PDSS and CASS parameters as the mean of V1 and V2 values on condition that values are prior to the first IMP intake (*i.e.* before or the same date as the first IMP intake date). In case of a visit missing value, the baseline will be equal to the non-missing value.
  - For other parameters, the last analysable value prior to the first IMP intake (*i.e.* before or the same date as the first IMP intake date).

Note: In case of patient randomised but not treated over the blind period: value at baseline is defined as the last analysable value prior or equal to the date of randomisation.

- Post-baseline value will be defined as any value recorded at a given timepoint after baseline.
- Change from baseline will be defined as the arithmetic difference between a post-baseline value and the baseline value for a given variable at a given time point.
- End value will be defined only for UNS, PDSS and CASS parameters as :

- The mean of V6 and V7 values. In case of a visit missing value, the End value will be equal to the non-missing value.

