## Analysis:

A negative Binomial Regression will be used according to the general model (section 2.2) for WRC estimated during the period V6-V7 (Justification Plazzi 2021) only in the type I Narcolepy patients (for other patients we don't have the baseline value). The WRC at baseline will be used as a fixed covariate and center as random (In case of non convergence of the model, this one can be updated).

The same way as the primary analysis (Including sensitivity analyses) will be performed: MAR and MNAR imputation and observed cases.

In addition,

- Descriptive statistics by treatment group during the following intervals: Baseline (D-28 to D0),
   Final DB last 6 weeks DB4=D21-D63 (i.e. V4-V7), Final DB last 2 weeks: DB2=D49-D63 (i.e. V6-V7) will be provided
- A supportive analysis will be to compare the proportion of patients such that WRC <1 between treatment groups (simple logistic regression providing OR with 95%CI)

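### The weekly cataplexy rate is divided by elapsed visit days, not completed diary evenings, so blank evenings count as zero episodes and imputation does not reach them

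*SAP*

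**What the plan says.** SAP 4.1.5.5 (patient sleep diary) defines WRC as episodes in the period over days in the period, times 7, rounded to an integer. The divisor is a difference of visit dates, "Number of days in the period= Date of the last visit of the period - Date of the first visit of the period", with 1 added. The same divisor serves the other weekly diary rates and mean night duration.

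SAP 4.5.3.2.3 uses WRC as an outcome: "A negative Binomial Regression will be used according to the general model (section 2.2) for WRC estimated during the period V6-V7", in type 1 patients only. It is also a covariate: "The WRC at baseline will be used as a fixed covariate and center as random". The general model in SAP 4.1.3.1 has no exposure term; it starts "Independent variables are (1) the baseline value of the studied endpoint" and adds only treatment and centre. SAP 4.1.3.2 makes WRC confirmatory by "testing the endpoints in the pre-defined order UNS, PDSS, UNS-CTP, WRC and MWT", each at two-sided 0.05.

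On missing data, SAP 4.1.5.1 states "Analysable value will be defined as any non-missing value". SAP 4.1.4.1 states "Missing data will be imputed for five main endpoints of this study (UNS, PDSS, UNS-CTP, WRC and MWT" and, for the jump-to-reference step, "In this study only one model will be used (for the endpoint value imputation". Neither document gives a rule for blank evenings, a minimum number of completed evenings, or a condition under which WRC becomes missing.

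The diary is meant to be filled in every evening from V0 to V8 (schedule footnote 4) and reviewed by the investigator at each visit (Protocol 3.7.1.2.6, SAP 4.5.3.2.3).

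**The concern.** Counting a blank evening as zero episodes is right only if it was left empty because nothing happened. The documents do not say that this is what a blank means, and the diary form is not shown. If evenings are blank for other reasons, the patient's rate is understated. If blanks are more common in one arm, the treatment ratio shifts with no drug effect behind it.

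The missing-data plan does not catch this. A partly filled diary yields a number, so the MAR, jump-to-reference and observed-case analyses all carry the same understated value.

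A distorted WRC could produce a false confirmatory claim on cataplexy. It could also produce a false failure, which would stop the sequence before MWT.

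**Working it through.** The documents state no rate, power or completion figure for WRC, so there is no figure of theirs to reproduce. The inputs are the SAP 4.1.5.5 formula and the planned visit days (V6 = D49, V7 = D56). Completion rates and episode rates are assumptions.

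**1. A blank equals a zero.** With E episodes on k completed evenings and divisor D, the SAP value is 7E/D. That is 7 times the daily mean over D days with the other D − k days set to 0.

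**2. Effect on one patient.** Assume one episode per evening (7 per week). At planned dates V6–V7 spans 7 days, so D = 8.
- 7 of 7 evenings completed: 7 × 7/8 = 6.125
- 5 of 7: 7 × 5/8 = 4.375
- 2 of 7: 7 × 2/8 = 1.75

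Per completed evening the rate is 7.0 each time. Two blanks leave 5/7 = 0.71 or 6/8 = 0.75 of the complete-diary value, for 7 or 8 evenings. SAP 4.5.3.2.3 also labels the window D49–D63. Over 14 or 15 evenings two blanks leave 12/14 = 0.86 or 13/15 = 0.87.

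**3. Effect between arms.** Expected ratio = true ratio × (completion on pitolisant / completion on placebo). With a true ratio of 1.00:
- averages of 2 vs 1 blanks: 5/6 = 0.83 or 6/7 = 0.86; in the longer window 12/13 = 0.92 or 13/14 = 0.93
- completion 70% vs 90%: 0.70/0.90 = 0.78; reversed, 1.29
- equal completion: 1.00

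**4. Null simulation.** 600 runs per scenario. Assumptions: 48 pitolisant and 24 placebo patients; patient rate gamma (shape 1, mean 1 per evening), multiplied in the end period by gamma (shape 2, mean 1); 14 complete baseline evenings; 8 end evenings over divisor 8; no centre effect; baseline adjusted as log(rate + 1). SAP rule: rounded WRC, no offset. Alternative: raw count with offset log(completed evenings).

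| Blanks, placebo / pitolisant | SAP rule: ratio (rejections) | Offset: ratio (rejections) |
|---|---|---|
| None | 1.010 (7.3%) | 1.011 (8.0%) |
| Random, 12.5% / 12.5% | 1.005 (7.2%) | 1.008 (7.0%) |
| Random, 12.5% / 25% | 0.864 (11.2%) | 1.008 (6.3%) |
| Random, 25% / 12.5% | 1.177 (11.2%) | 1.011 (7.2%) |
| Episode-free evenings only, 25% / 25% | 1.010 (7.3%) | 1.010 (6.7%) |
| Episode-free evenings only, 25% / 50% | 1.010 (7.3%) | 1.152 (12.7%) |

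The reference is the complete-diary rejection rate, not 5%. The excess under unequal random blanks is 11.2 − 7.3 = 3.9 points. The Monte Carlo standard error √(p(1 − p)/600) is about 1.0 point at p = 0.063 and 1.4 at p = 0.127.

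**5. The added day.** Visits are in the morning if possible (Protocol 5.2), and the V6 diary covers evenings until the next visit (Protocol 5.2.7). V6–V7 then holds 7 evenings (D49–D55) against a divisor of 8, so a complete diary gives 7/8 = 0.875 of the true rate. This applies to both arms, so the ratio is unaffected.

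**6. Secondary points.**
- Rounding turns 1 episode in a 15-day baseline (7/15 = 0.47), or 1 or 2 in a 29-day baseline (0.24, 0.48), into 0. It makes the supportive WRC <1 criterion mean an unrounded value below 0.5, and the window for that criterion is not named.
- For night duration the divisor cannot be right: seven assumed 9-hour nights give 63/8 = 7.9 h with a complete diary, and two blanks give 45/8 = 5.6 h.

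**The case against.** **The better divisor depends on why evenings are blank.** A database check shows that an evening is blank, not why. If only episode-free evenings are skipped, the offset is the biased version (1.15, 12.7% rejections) and the SAP rule is not. This stands. It is the reason to pre-specify one version and report the other. It does not defend leaving the choice unstated. The use of the same divisor for night duration also suggests that it was not chosen as a blank-means-none convention.

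**Unequal completion is speculative.** The trial is double-blind with identical visits and diaries, and investigators review each diary with the patient. No document points to a difference between arms. This stands as to size. Review should reduce blanks, but it is not a rule for those that remain. Protocol 5.2.18 also allows phone visits in place of site visits during the pandemic.

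**A convention may exist elsewhere.** The diary form, the CRF or the data management plan may define an empty field. That is possible, and the fix begins by checking it.

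**That imputation skips blank evenings is an inference.** The SAP never says so in words, and the single-model sentence in 4.1.4.1 concerns only the jump-to-reference step. The inference rests mainly on the definition of an analysable value and on imputation being directed at missing evaluations. Nothing in either document points the other way.

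**The added day can be read consistently.** If the V7-day evening, recorded in the next diary, is counted, D49–D56 holds 8 evenings. The SAP does not say which reading applies.

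**Conclusion.** The concern holds. The divisor is explicit, and the zero scoring of blank evenings follows by arithmetic. No rule in either document corrects it.

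Its reach is limited. With equal or full completion the treatment ratio is not biased. WRC is tested only if UNS, PDSS and UNS-CTP succeed, and only in type 1 patients. The primary result is untouched. Size and direction cannot be known without completion rates. The illustrations run from no effect to a ratio of 0.78 or 1.29 under an assumed 20-point gap in completion, and they shrink if the window is 14–15 days.

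A confirmatory result should still not turn on an unstated convention for unrecorded evenings. This should be fixed before unblinding. Confidence is medium, because the diary form and the actual completion are not available.

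**What to change.** Before unblinding, establish whether the database separates a blank evening from a zero entry.

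**If it does:**
- model the raw V6–V7 episode count by negative binomial regression with offset log(completed diary evenings), and use an unrounded baseline rate per completed evening as covariate
- count the same evenings in numerator and denominator, and state whether visit-day evenings belong to the period
- treat a wholly blank window as missing and handle it under SAP 4.1.4.1
- tabulate completed evenings by arm and period
- keep the elapsed-day version as a sensitivity analysis

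**If it does not:** keep the elapsed-day divisor and state the assumption that a blank means no episode.

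In either case, round only for display, name the window for the WRC <1 comparison, and reconcile the D49–D63 label with V6–V7 (D49–D56). Divide night duration by completed nights.

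The cost is SAP wording, code and the blank-versus-zero check. Patients with few entries will carry less weight. The offset assumes that blank evenings have the same rate as completed ones and is biased if families skip only episode-free evenings, so the elapsed-day version should be reported beside it.

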5.2.7. V6 – Control treatment visit (Day 49 ± 2 days)

A complete interrogation including occurred of possible adverse events and concomitant

medication used will be done and recorded,

A physical examination including vital signs shall be carried out,

12-lead ECG recording with calculation and control of QTcF,

The following questionnaires should be performed:

- PDSS,

- CASS,

- CDI,

- C-SSRS,

- UNS,

- TEA-Ch,

- Clinical Global Impression of Change (CGI-C) on EDS and on cataplexy,

- Retrieval of sleep diary of the previous visit and check by the investigator. Delivery of one

other sleep diary which have to be completed every evening until the next visit.

No dispensation performed at V6.

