5.2.8. V7 – End of Double Blind period (Day 56 ± 2 days)

This visit should be **imperatively** done in the morning (around **9.30 a.m.**) and all further visits

should be done at the same time of day, if possible, to ensure identical evaluation conditions

along the study.

Patients will be required to have sufficient nocturnal sleep (minimum 6 hours) and not

drink alcohol during the night prior to this visit. An optional polysomnography can be done in

accordance with the processes of sites, the evening preceding the MWT test to confirm a sufficient

nocturnal sleep. The patient will be required to take a light breakfast before 8.00 a.m. and arrive

at the trial center around 9.00 a.m. They should refrain from drinking any stimulatory beverage

such as coffee, tea or Coca-Cola this morning until the end of this visit.

The first session of MWT will approximately start at 10.00 a.m.

A complete interrogation including occurred of possible adverse events and concomitant

medication used will be done and recorded,

A physical examination including vital signs shall be carried out,

12-lead ECG recording with calculation and control of QTcF,

A blood sample will be taken for routine haematological and biochemical test (including β-

HCG pregnancy test for pubescent female) and semi-quantitative urinalysis (dipstick),

A urine drug testing (for patients from 12 years),

The following questionnaires should be performed:

- PDSS,

- CASS,

- C-SSRS,

- UNS,

- CGI-C on EDS and on cataplexy,

EudraCT number: 2013-001506-29

- Retrieval of sleep diary of the previous visit and check by the investigator. Delivery of one

other sleep diary which have to be completed every evening until the next visit,

-Patient's Global Opinion on the effect of investigational treatment if able to express himself.

If not will be reported either by parents or teachers.

Investigational treatment allocation: start 1-week wash-out period.

The treatment pack bring back from previous visit by patient is checked by investigator for the

compliance.

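### The SAP rounds the weekly cataplexy rate (WRC) to an integer before applying the WRC <1 cut, so the cut actually applied is a raw rate below 0.5 per week

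*SAP*

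**What the plan says.** SAP 4.1.5.5 (Efficacy data, patient sleep diary) defines three weekly ratios: WRC, sleep attacks and severe sleepiness (NSAE), and hallucinations and sleep paralysis (NHS). Each is "Number of episodes of the concerned parameter in the period / Number of days in the period", multiplied by 7. The number of days is "Date of the last visit of the period - Date of the first visit of the period + 1". The definition closes with "Results are rounded to to the nearest integer number".

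SAP 4.5.3.2.3 analyses "WRC estimated during the period V6-V7" by negative binomial regression in type 1 patients, with baseline WRC as a fixed covariate. It adds a supportive analysis to "compare the proportion of patients such that WRC <1 between treatment groups", by "simple logistic regression providing OR with 95%CI". The sentence on the cut names no period and does not say that an unrounded rate is used. The same section lists an interval D49-D63 and equates it with V6-V7, although the visit schedule places V7 at D56 and V8 at D63.

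SAP 4.1.3.2 places WRC fourth in the fixed sequence, after UNS, PDSS and UNS-CTP. The WRC <1 comparison is not in the sequence.

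**The concern.** The derivation and the cut do not fit together. Once WRC is an integer, WRC <1 can only mean WRC = 0, and every raw rate from 0.5 up to 1 has become 1 and fails. A program that follows the SAP literally would report a proportion and an odds ratio labelled WRC <1 that belong to a stricter criterion.

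The rounding reads as part of the variable and not as a display rule. It stands in the derived-variables section, to which SAP 4.5 refers for the definitions of derived parameters. Decimals for presentation are set separately in SAP 4.1.2. In the same diary block, night duration is rounded to one decimal, so whole-number rounding was specified for these three ratios in particular.

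The same variable is named for the negative binomial model, so the loss of detail reaches a tested secondary endpoint as well.

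**Working it through.** **Inputs.** WRC = round(7k/d), with k episodes and d = last visit − first visit + 1 (SAP 4.1.5.5). The cut is WRC <1 (SAP 4.5.3.2.3). V6 is D49 ± 2 and V7 is D56 ± 2 (Protocol 5.2.7 and 5.2.8).

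**Effective cut.** round(7k/d) < 1 requires round(7k/d) = 0, that is, 7k/d < 0.5. (At exactly 0.5 the result depends on the tie convention, which the SAP does not state. With one episode this arises only at d = 14.)

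**Period length for V6-V7 by visit dates.** Nominal: 56 − 49 + 1 = 8. Shortest: 54 − 51 + 1 = 4. Longest: 58 − 47 + 1 = 12.

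**Largest episode count that meets WRC <1:**

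| Period | d | One episode, 7/d | Rounded | Max k, unrounded | Max k, rounded |
|---|---|---|---|---|---|
| V6-V7, shortest | 4 | 1.75 | 2 | 0 | 0 |
| V6-V7, nominal | 8 | 0.875 | 1 | 1 | 0 |
| V6-V7, longest | 12 | 0.583 | 1 | 1 | 0 |
| D49-D63 label | 15 | 0.467 | 0 | 2 | 1 |
| V4-V7, D21-D56 | 36 | 0.194 | 0 | 5 | 2 |

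For every d from 4 to 12, only k = 0 passes after rounding. Without rounding, k = 1 fails for d = 4 to 7 and passes for d = 8 to 12. The two rules therefore differ at the nominal schedule and at every longer V6-V7 interval.

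**Size of the shift (assumed distributions; the documents give none).** With Poisson counts over 8 days the mean is 8/7 × the weekly rate. The unrounded rule admits P(K ≤ 1) and the rounded rule P(K = 0):

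- 0.5 per week: 0.89 against 0.57
- 1 per week: 0.68 against 0.32
- 2 per week: 0.33 against 0.10

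**Effect on the odds ratio (also assumed).** Take negative binomial counts in an 8-day period, dispersion 1, means m = 1.5 and 3. Then P(K = 0) = 1/(1 + m) = 0.40 and 0.25, and P(K = 1) = m/(1 + m)² = 0.24 and 0.1875.

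- Unrounded: 0.64 against 0.4375; OR = (0.64/0.36)/(0.4375/0.5625) ≈ 2.3.
- Rounded: 0.40 against 0.25; OR = (0.40/0.60)/(0.25/0.75) = 2.0.

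**Negative binomial analysis.** At d = 8, 4 and 5 episodes give 3.5 and 4.375, and both become 4. If baseline is the D-28 to D0 interval that SAP 4.5.3.2.3 lists, d = 29. One or two episodes then give 0.24 or 0.48, and both become 0.

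**The case against.** - **Order of steps.** The SAP does not spell out that rounding precedes the cut. That is true, but WRC is defined as the rounded result and nothing exempts the responder analysis.
- **No patient with an episode could pass.** A reader might infer this as an absolute. It holds only if V6-V7 means the visit dates. Under the SAP's own D49-D63 label (d = 15) one episode rounds to 0 and passes. The Protocol's secondary endpoints also speak of two end-of-treatment weeks. The effective cut of 0.5 stands either way; the zero-episode reading is conditional.
- **The added day.** From D49 to D56 there are seven diary evenings before the V7 visit. One episode in seven days is exactly 1.0 and fails WRC <1 with or without rounding. It becomes 0.875 only because the SAP counts both visit days. This stands: deleting the rounding and leaving the day count unchecked would let one episode in a nominal week pass.
- **Different meanings at baseline and at the end.** A reader might infer that the cut shifts between the two. SAP 4.5.3.2.3 compares treatment groups and applies no cut at baseline. The unrounded maximum also varies with period length, so that variation is not peculiar to rounding.
- **Reach.** The comparison is supportive, and in the assumed example the odds ratio moves only from about 2.3 to 2.0, in the same direction. Both points stand and limit the consequence. They do not make the label correct.

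**Conclusion.** The point holds as an inconsistency between SAP 4.1.5.5 and 4.5.3.2.3. The criterion is stated as fewer than one episode per week, and the derivation delivers fewer than 0.5. That conclusion needs no distributional assumption, only that WRC in the cut is WRC as derived.

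By visit dates the practical difference is one episode: zero allowed instead of one, for periods of 8 to 12 days. Under the D49-D63 label it is one instead of two. The proportions reported could change substantially (0.68 to 0.32 at an assumed Poisson rate of 1 per week), while the odds ratio may change little.

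A reader might infer that type I error is compromised. The documents do not support that: the WRC <1 comparison lies outside the fixed sequence. For the fourth-ranked WRC test, what is shown is loss of information in the outcome and the baseline covariate; its effect on that test has not been quantified. The change should be made, but it does not threaten the primary analysis.

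**What to change.** 1. In SAP 4.1.5.5, delete the whole-number rounding for WRC, NSAE and NHS. Any rounding for tables belongs with the display rules.
2. In SAP 4.5.3.2.3, apply WRC <1 to the unrounded rate over one named period. Reconcile V6-V7 with D49-D63, and check that the added day matches the diary days actually covered.
3. Alternatively, if freedom from cataplexy is what is intended, state zero episodes in the named period as the criterion. The choice should be made before unblinding, because choosing between the two cuts afterwards would be data-driven.
4. In the negative binomial model, use the raw episode count as the outcome with log(days) as offset, and an unrounded baseline rate as covariate. If rounding was meant to supply integers for the count model, raw counts do this without loss.

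The cost is SAP wording and programming. No new data are needed.
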